10.3.5.2 Safety endpoints

The objective of the evaluation is to investigate safety and tolerability of MCI-186. All safety and tolerability variables will be listed and summarized descriptively. There will be no formal statistical analysis of the safety data. In general, safety data will be summarized separately by each group (Group 1, 2 and 3) and/or day, as appropriate.

10.3.5.3 Adverse events

Adverse events will be coded using MedDRA (version 18.1 or later). A by-subject AE data listing including start/stop times, verbatim term, Preferred Term, System Organ Class (SOC), dose level, severity, seriousness, relationship to treatment and outcome will be provided. All AEs that start before dosing will be classified as baseline AEs and will be listed only. All treatment-emergent AEs (TEAEs), i.e., AEs which start on or after dosing,

will be tabulated. In the tabulations, numbers of subjects with TEAEs and numbers (occurrences) of TEAEs will be counted separately.

The following summaries of TEAEs will be presented:

- Summary of AEs by SOC and Preferred Term
- Summary of AEs by SOC, Preferred Term and severity of event
- Summary of AEs by SOC, Preferred Term and relationship to treatment

The above TEAEs summaries will be produced by time interval as appropriate.

In addition, details of AEs and SAEs leading to withdrawals will be listed separately.

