4.5 Withdrawal of individual subjects

A subject will be withdrawn if ANY of the following criteria are met:

- The subject wishes to withdraw from further participation
- The subject is significantly noncompliant with the Protocol
- The subjects is discontinued due to safety reason; continuing in the study would be detrimental to the subject's safety in the opinion of the Investigator, such as
 - The subject experiences intolerable AEs or SAEs
 - The subject has clinically significant changes in safety parameters at any of the post-dose time points, as confirmed with a repeat assessment performed as soon as possible after the initial out-of-range result

In addition, a subject may be withdrawn at any time for any reason other than those listed here.

If a subject is discontinued prematurely from the study, the date the subject is withdrawn from the study and the reason for withdrawal will be recorded on the CRF.

In case of withdrawal of a subject, the Follow-up Visit assessments should be performed, as far as possible (Section 5.2.3).

Any withdrawal due to an AE or for any safety reason should always be considered serious.

Any unresolved AE or SAE will be followed up according to Section 8.9.

In the event that a subject elects not to return to the study center for the end of study visit, the Investigator must make every effort to contact the subject to review all AEs. In the event that a subject drops out of the study at any time, the reason for discontinuation must be fully documented in the source documents and the CRF. The study center personnel will document the AEs and any other assessments in the source documents and will make every effort to complete all required end of study assessments.

Subjects withdrawn for non-treatment-related reasons may be replaced at the discretion of the Sponsor and Investigator. Replacement subjects will receive the treatments intended for the withdrawn subject.

Criteria for amendment of dose in subjects with mild renal impairment (Group 1)

The subjects with mild renal impairment will be treated first. The second subject with mild renal impairment will not be treated until the completion of review for safety and PK profile in the first treated subject by the Sponsor and the Investigator. [REDACTED]

[REDACTED]

Procedure and criteria for starting treatment of subjects with moderate renal impairment (Group 2)

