8 ADVERSE EVENT MANAGEMENT

All AEs and SAEs will be recorded in the source documents. All AEs and SAEs that occur from the time written informed consent is obtained until the end of the Safety Follow-up Period will be recorded in the CRF. Even if the AE is assessed by the Investigator as not related to IMP, its occurrence must be recorded in the source documents and CRF. AEs will be classified as 'baseline' if they occur before the administration of IMP. AEs will be classified as 'treatment-emergent' if they arise following the first administration of IMP or if a pre-dose AE increases in severity following dosing.

At each study visit, after the subject has had an opportunity to spontaneously mention any problems, the Investigator should inquire about the occurrence of AEs. The questioning should be open-ended and non-leading.

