8.6 Recording and reporting of adverse events

All AEs, regardless of the relationship to IMP, occurring from the time written informed consent is obtained from a subject until the end of the safety Follow-up Period or the withdrawal of the subject from the study will be recorded.

All AEs will be recorded on an AE form in the CRF. Reports should contain a description of the event, date and time of onset, date and time of resolution, severity, treatment required, relationship to IMP, action taken with the IMP, outcome and whether the event is classified as serious.

The Investigator will evaluate the severity of the AEs (as defined in Section 8.3) and will assess the causality between the AEs and the IMP (as defined in Section 8.4).

Pre-existing illnesses, which started prior to entry and is still ongoing at the start of the study, will not be considered AEs unless they worsen during the treatment period. Pre-existing conditions will be recorded as medical history.

If the Investigator becomes aware of any new safety information, or any safety information which appears to be either study or IMP related after the final Follow-up Period, then they must notify the Sponsor immediately.

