7.9.1 Adverse Events

All AEs for each subject, including multiple occurrences of the same event, will be presented in full in a comprehensive listing including subject number, treatment, severity, seriousness, action taken, outcome, relationship to treatment, onset/stop date and duration. Deaths that occur during the study will be listed.

Duration of the AE and time to the AE occurrence from start of the IMP will be calculated and presented in days (duration = AE stop date – AE start date + 1).

AEs which start on or after dosing that are expressed or exacerbated are defined as treatment emergent adverse events (TEAEs).

The frequency and incidence of TEAEs will be summarized by System Organ Class (SOC) and Preferred Term (PT). The summary will be sorted by International Agreed Order (IAO) for SOC and alphabetical order for PT (or by frequency from the highest to the lowest).

Following summaries of TEAEs will be presented:

- Summary of AEs by SOC and PT
- Summary of AEs by SOC, PT and severity of event
- Summary of AEs by SOC, PT and relationship to treatment

For summaries of AEs multiple occurrences of the same event within a subject will be counted once in the summaries by SOC and PT; multiple occurrences of the same event within a subject will be counted once in the maximum intensity category (severe > moderate > mild) and/or maximum drug relationship category (reasonable possibility > no reasonable possibility). If intensity or relationship is found to be missing the most severe occurrence will be imputed for that particular summary.

Proportion of subjects with any TEAE, subjects with any related TEAE, subjects with any treatment emergent SAE, and subjects with any TEAE leading to discontinuation of the study will be summarized.

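### Protocol 8 and Protocol 10.3.5.3 disagree on whether a pre-dose adverse event that worsens after dosing is treatment-emergent, and SAP 7.9.1 does not settle it

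*Protocol*

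**What the plan says.** Protocol 8 classes an AE as baseline if it occurs before the study drug is given. It then counts an AE as treatment-emergent if it arises after the first administration, "or if a pre-dose AE increases in severity following dosing".

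Protocol 10.3.5.3, which sets out the AE tables, has no worsening exception: "All AEs that start before dosing will be classified as baseline AEs and will be listed only". It explains treatment-emergent AEs (TEAEs) as "i.e., AEs which start on or after dosing", and only these are tabulated.

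SAP 7.9.1 has its own sentence: "AEs which start on or after dosing that are expressed or exacerbated are defined as treatment emergent adverse events (TEAEs". The same section asks for "Proportion of subjects with any TEAE, subjects with any related TEAE, subjects with any treatment emergent SAE", and also for subjects with a TEAE leading to discontinuation. That makes four subject proportions, all resting on the TEAE flag.

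SAP 8, the section for changes from the protocol, declares none. AEs are collected from informed consent onward (Protocol 8 and 8.6), so pre-dose AEs will be in the database.

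**The concern.** The same event is tabulated under one protocol section and only listed under another. The wording of Protocol 10.3.5.3 covers every AE with pre-dose onset, so it cannot be read as carrying the Protocol 8 exception silently.

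Safety and tolerability is the secondary objective, and the TEAE tables are its main summary. SAP 11 relies on double programming, which needs a single rule. As the text stands, two competent programmers could build different flags and each cite the plan. Protocol 10.3.1 requires the SAP to be approved before database lock. Settling the definition by then avoids choosing it when the affected events are already known.

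**Working it through.** **Step 1: the definitions side by side.** There is no sample-size or power figure to reproduce here, so the check is a comparison of the texts.

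| Event | Protocol 8 | Protocol 10.3.5.3 | SAP 7.9.1 |
|---|---|---|---|
| Starts after dosing | TEAE | TEAE | TEAE |
| Starts before dosing, does not worsen | Baseline | Baseline, listing only | Not a TEAE |
| Starts before dosing, worsens afterwards, kept as one record | TEAE | Baseline, listing only | No, if the onset condition is read strictly; yes, if *exacerbated* is meant to override it |
| As above, but worsening entered as a new record with post-dose onset | TEAE | TEAE (new record) | TEAE (new record) |

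Only the third row is in conflict. The fourth row shows that a recording rule would remove the conflict, but neither document states one.

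**Step 2: which events fall in the third row.** Under Protocol 8.6, illnesses that began before entry "will not be considered AEs unless they worsen during the treatment period". Such an illness therefore first becomes an AE when it worsens, and its natural onset is then post-dose, although Protocol 8.6 gives no onset-date rule. That leaves AEs which

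- arise between consent and dosing,
- are still ongoing at dosing, in a subject who passes the eligibility checks on Day -1 and before dosing on Day 1 (Protocol 5.2.2), and
- then worsen between dosing and the Day 7 (+2 days) visit.

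**Step 3: size of one such event.** The planned groups are 11, 8 and 11 (Protocol 3.1), and 11 + 8 + 11 = 30 matches the stated total. The safety set is all dosed subjects (Protocol 10.2). If all planned subjects are dosed, one subject counted or not counted is

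- Group 2: 1/8 = 12.5%
- Groups 1 and 3: 1/11 = 9.1% each

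The any-TEAE proportion moves by this amount only if the subject has no other TEAE.

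**Step 4: which proportions can move.** Any TEAE is affected directly. The related, serious and discontinuation proportions move only if the event also has those attributes. Protocol 4.5 says "Any withdrawal due to an AE or for any safety reason should always be considered serious", so a worsened AE that leads to withdrawal would count as serious under that sentence, although the definition in Protocol 8.2 does not name withdrawal as a criterion. All four proportions move only if one event is related, is serious and leads to withdrawal.

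The documents give no rate for such events, so no expected count can be computed.

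**The case against.** The strongest reply is that the SAP already means what Protocol 8 says. If onset at or after dosing were a strict condition, *exacerbated* would seem to add nothing. The reading that gives the word work to do is that an AE first appears or gets worse after dosing. On that view SAP 8 can rightly declare no change, and only a clarifying line is needed. Further, safety is descriptive with no formal analysis, every AE is listed in full, and in a study of 30 subjects a reader can find any affected event.

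Most of this stands, and it is why the point is minor. It does not close the gap. The onset condition is still in the sentence, and *exacerbated* could equally refer to pre-existing illnesses that become AEs on worsening under Protocol 8.6. Declaring no change cannot show which of two conflicting protocol sections was followed.

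Several stronger conclusions are tempting but not supported:

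- A reader might infer that the case report form cannot capture worsening, because Protocol 8.6 asks for "date and time of onset, date and time of resolution, severity, treatment required, relationship to IMP" and no date of a severity change. That list says what reports should contain. The form and its completion guidelines are not in the documents, so a missing field cannot be shown.
- A reader might infer from the length of screening that many events are affected. Calendar time before dosing is not a risk, and the eligibility re-checks will screen out some subjects with ongoing AEs.
- A reader might infer a bias between groups, since impaired subjects may have stable concurrent disease and controls must be healthy. Without event rates, neither size nor direction can be stated.
- A reader might add SAP 7.9.6, which leaves discontinuation assessments out of summaries, and infer that withdrawn subjects vanish from the safety tables. They do not: SAP 7.9.1 still summarizes TEAEs leading to discontinuation, and keeping off-schedule values out of by-visit summaries is defensible.

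**Conclusion.** The contradiction between Protocol 8 and Protocol 10.3.5.3 is real. Following the latter as written leaves out of the tables events that the protocol itself defines as treatment-emergent. SAP 7.9.1 leans towards Protocol 8 but does not decide the matter.

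The importance is minor. The effect is one subject at a time, with the percentages shown above. These assume that the planned numbers are dosed, that the worsening is kept under the original pre-dose record, and that the subject has no other TEAE. There may be no such event in the study. The AE listings and the primary pharmacokinetic comparison are unaffected.

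**What to change.** In SAP 7.9.1, define a TEAE as an AE that begins at or after dosing, or that begins before dosing and becomes more severe after it, as Protocol 8 does. State how worsening is identified, for example by a new AE record with its own onset date. In SAP 8, replace the statement that there are no changes with a note that this definition supersedes the wording of Protocol 10.3.5.3. Carry the same note into the study report, as Protocol 10.3.1 requires for departures from the planned analysis.

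The cost is a sentence or two in each SAP section and a small change to the TEAE flag. A few data queries may be needed to date the worsening of pre-dose AEs, and TEAE counts may rise slightly. Making the change in the SAP rather than the protocol avoids the notification, and possible ethics review, that Protocol 11.2.3 attaches to protocol amendments.

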10.3.5.4 Vital signs and electrocardiograms

Vital signs and 12-lead ECG variables and changes from baseline will be summarized (N, n, mean, SD, median, minimum and maximum) at each time point by each group (Group 1, 2 and 3).

The baseline for the vital sign parameters and 12-lead ECG measurements will be the last valid assessment obtained on Day 1 prior to the administration of IMP (Day 1, pre-dose).

10.3.5.5 Routine safety laboratory tests

Laboratory variables and changes in laboratory variables from baseline will be summarized (N, n, mean, SD, median, minimum and maximum) at each time point for each group (Group 1, 2 and 3). Baseline will be Day -1 assessment.

Urinalysis variables will be listed by subject and time point.

Values outside the normal ranges (provided with the laboratory report), will be flagged in the subject data listings.

10.3.5.6 Prior and concomitant medication

Prior and concomitant medication will be coded according to the WHO DD using the current version and Anatomical Therapeutic Chemical (ATC) classification system. These categories will be tabulated and summarized by each group (Group 1, 2 and 3). Incidence tables will be summarized with ATC level 2 code and text (e.g. 'N02 – Analgesics') and preferred name for each group (Group 1, 2 and 3). Prior and concomitant medications will be listed by subject including the full ATC code, text, and Preferred Term.

Prior or concomitant medication data will be summarized by each group.

10.3.5.7 Physical examination

Physical examination data will be listed by subject. Changes in physical examinations will be described in the text of the CSR.

10.3.6 Analysis of exploratory endpoint(s)

Not applicable in the study.

10.3.7 Interim analysis

Not applicable in the study.

11 STUDY MANAGEMENT AND ETHICAL AND REGULATORY REQUIREMENTS

11.1 Good Clinical Practice

The Investigator will ensure that this study is conducted in compliance with the 2013 (Fortaleza, Brazil) revision of the 1964 Declaration of Helsinki. This study will also be conducted in accordance with Good Clinical Practice (GCP) requirements described in the current revision of International Conference on Harmonisation of Technical Requirements of Pharmaceuticals for Human Use (ICH) Guidelines and Japan-GCP. This study will also be carried out in accordance with regional and local legal requirements. Before the first subject is enrolled in the study, all ethical and legal requirements will be met.

11.2 Investigator responsibilities

11.2.1 Informed consent

The investigator will prepare an ICF. The ICF will be submitted to the Sponsor, and approved by the IRB prior to the start of the study.

Prior to undergoing any study-specific procedure, all legally competent subjects must consent in writing to participate. An ICF will be given to each subject, which will contain all regulatory-required elements, all ICH-required elements, and data protection information, when applicable, in language that is understandable to the subject.

The process of obtaining the informed consent will be in compliance with all regulatory regulations, ICH requirements, and local laws.

Either the Investigator or a designated person, qualified to meet any applicable local regulations, who is equally knowledgeable about the study will explain the aims, methods, anticipated benefits and potential hazards of the study and any discomfort it may entail. The review must be in a form understandable to the subject. A corresponding written explanation will also be provided and the subject allowed sufficient time to consider the study information.

If the subject is willing to participate in the study, the ICF will be sealed with printed name or signed and dated by the subject, the Investigator and, if applicable, the designated person who explained the nature of the study. The subject will receive a copy (together with the information sheet) and the original ICF will be retained with the study records at the study center.

The date (and time, if required) on which the ICF is signed by the subject must be recorded in the source notes.

The Investigator or his/her designee must emphasize to the subject that study participation is entirely voluntary and that consent regarding study participation may be withdrawn at any time without penalty or loss of benefits to which the subject is otherwise entitled.

If the ICF is amended during the study, the Investigator must follow all applicable regulatory requirements pertaining to approval of the amended ICF by the IRB. The study center personnel must use the amended ICF for all new subjects and repeat the consent process with the amended ICF for any ongoing subjects.

11.2.2 Contact to other attending physicians

The investigator (or subinvestigator) will confirm during the Screening period whether subjects have medical attention by other doctors. When subjects are visiting his/her doctors, the investigator (or subinvestigator) will inform his/her doctors of the participation in the study upon his/her consent. In addition, the investigator, subinvestigator or the investigational staff will issue a study participation card to the subjects and instruct them to present the card to doctors when subjects visit other hospitals.

11.2.3 Ethical and regulatory approval

The study must be conducted in accordance with ethical principles that have their origins in the Declaration of Helsinki and that are consistent with Law for Ensuring the Quality, Efficacy, and Safety of Drugs and Medical Devices, ICH-GCP, Japan-GCP and the protocol. The Investigator and Sponsor will sign this Protocol to confirm agreement to abide by it.

Before any study-related procedure is performed on a subject, IRB, regulatory and local approvals of this Protocol will be obtained. While the study is ongoing and at study completion/discontinuation, the Sponsor or Investigator will submit information to the IRB(s) in accordance with institutional/local regulations, for example:

- Information on SUSARs
- Periodic reports on the progress of the study
- Notification of the end of study or early termination
- Final study summary upon completion or closure

The Sponsor will ensure that any SUSARs from this study and other studies with this IMP are reported promptly to the regulatory authorities.

If it is necessary to amend the Protocol during the study, proper notification will be made to the IRBs or Regulatory Authority depending on the nature of the modification. Protocol Modification requiring IRB approval may be implemented only after a copy of the IRB's approval/favourable opinion letter has been transmitted to the Sponsor. Protocol Modification that is intended to eliminate an apparent immediate hazard to subjects may be implemented prior to receiving Sponsor and IRB approval. However, in this case, approval must be obtained as soon as possible after implementation.

Any Protocol or other deviations that occur during the study will be documented and reported to the Sponsor by the Investigator. Depending on the nature of the deviation, this may be reported to the appropriate Regulatory Authority, the Head of the study center and the IRB.

The Investigator and the Sponsor should sign the protocol to confirm agreement. Before implementing the study, the protocol and any other appropriate documents must be reviewed and approved by the IRB and the appropriate Regulatory Authority.

The Head of study center will forward to the Sponsor or Investigator a copy of the written approval of the IRB and any other approving bodies.

11.2.4 Source document requirements and document access during the study

The Investigator or a designated person by the Head of study center must retain a comprehensive and centralized filing system of all study-related documentation (including, but not limited to: essential documents, copies of Protocols, CRFs, source data such as original reports of test results, IMP dispensing logs, correspondence, records of informed

consent, and other documents pertaining to the conduct of the study) that is suitable for inspection by the Sponsor and representatives of regulatory authorities.

The Investigator/institution will permit study-related monitoring, audits, IRB reviews and regulatory inspections providing direct access to source data/documents.

